4.1. Overall Description of Trial Design

This is a multi-center, double-blind, randomized, placebo-controlled, single dose, dose ranging study in healthy, breastfeeding, female volunteers (≥ 18 years). The study will randomize 76 subjects and their breastfed infants aged >30 days to 11 months of age into three arms.

After reviewing and signing an informed consent, the subjects will undergo screening assessments to determine study eligibility up to a 45-day Screening Period.

On Day 1 of the randomized portion, subjects will be randomized in a 2:2:1 ratio to one of the three treatment arms to receive active vaccine at medium dose or high dose or placebo, as follows (Figure 1):

Figure 1

All subjects will be monitored for Solicited Symptoms of Reactogenicity (GI and systemic) for 1 week following the study drug dose and unsolicited AEs for 28 days post study drug dose (until Day 29) during the Active Period. Subjects will then enter the Follow-up period after Day 29 and will be monitored for specified unsolicited adverse events (SAEs, AESIs, and NOCIs) through Day 365 (Month 12) for safety and durability of immune response. Subjects will have samples (nasal, saliva, and serum) collected at the site, and will also self-collect samples (breastmilk and infant stool) at home for evaluation of immunogenicity as specified in the SoA (Table 1).

Table 2 Study Design

Treatment Group	Study Drug	Per Strain Dose (IU) +/- 0.5 log	Total Dose (IU/dose)	Dosing Schedule	No of Subjects
Arm 1 (n=30)	Bivalent GII.4/GI.1 vaccine	5×10^{10}	1×10^{11}	Day 1	30
Arm 2 (n=30)	Bivalent GII.4/GI.1 vaccine	1×10^{11}	2×10^{11}	Day 1	30
Arm 3 (n=16)	Placebo	N/A	N/A	Day 1	16
Total					76

Abbreviations: IU=infectious units

After vaccination on Day 1, the study will include an Active Study Period that runs through 4 weeks after administration (Day 29), and a Follow-up Period of one year for safety and duration of immune response. Study assessments will be conducted as shown in the SoA ([Table 1](#)). In addition, subjects will be contacted by phone between site visits to monitor for safety as specified in the SoA ([Table 1](#)).

A subject is considered to have completed the study if she completes the study active period at Day 29 (End of Study Active Period). Following completion of the Day 29 visit by all subjects the database will be cleaned and locked and the study unblinded. The Clinical Study Report (CSR) will be written based on the Day 29 dataset.

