- Collect a blood sample to determine the subject's Human Immunodeficiency Virus (HIV), Hepatitis B Virus (HBV), and Hepatitis C Virus (HCV) status.
- If the subject and her infant pass all the inclusion and exclusion criteria at the end of the screening visit:
 1. Provide a manual breast pump set. Teach the subject how to use a manual breast pump properly.
 2. Provide kits with instructions for breastmilk sample collection, storage, and return. Teach the subject how to express breastmilk to provide a total of 10 ml of breastmilk from the right breast for each sample collection. Instruct the subject to consistently collect breastmilk samples from the right breast. (The subject can use a manual or electric breast pump if she does not wish to manually express her breastmilk. If the subject is unable to express or pump breastmilk from the right breast, she can collect breastmilk from the left breast and must consistently collect breastmilk samples from the left breast.)
 3. Provide kits with instructions for infant stool sample collection, storage, and return. Teach the subject how to properly collect the infant stool sample and store it until the samples are ready to be shipped.
 4. Timepoints for breastmilk and infant stool sample collection must be thoroughly discussed with the subject. The subject must collect breastmilk sample and infant stool sample (15ml) at baseline prior to the first dose (Day - 2 to Day 1).

7.1.2. Procedure to be followed during Active Study Period (Day 1 to Day 29)

It is anticipated that the procedures below will be conducted in a stepwise manner; ensuring that procedures listed prior to administration of the vaccine are conducted prior to that administration. The site does not need to wait the full 45 day screening period to start the active study period for the subject.

- The Principal Investigator will ensure that all inclusion criteria and none of the exclusion criteria for the subject and her infant are met on Day 1.
- Ensure the subject collected baseline breastmilk sample (10ml) and infant stool sample between D-2 to D1. Review with the subject how the collection was done and if the samples were properly stored, prior to vaccination. If this was not done, the subject will need to reschedule the dosing visit ASAP and be reminded to collect baseline samples prior to the rescheduled visit.
- A urine pregnancy test will be done for all subjects; site must confirm negative result before dosing.

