- Perform an alcohol test and site must confirm negative result before dosing.
- Vital signs will be obtained, including temperature, blood pressure, pulse rate and respiratory rate after resting in a sitting position for at least 5 minutes.
- A targeted, and symptom-directed physical examination will be done for all subjects during the active study period visits. At a minimum, assessments of the skin, respiratory system, cardiovascular system, and GI (abdomen, liver, and spleen) will be included.
- The subject's randomization number will be noted.

- Collect blood, nasal and saliva samples for Immunogenicity assessment prior to study drug administration.
- Site staff member(s) will dispense/administer the investigational product. Please refer to the Pharmacy Manual for further instruction on this process.
- Prior to study drug administration on Day 1, the subject's temperature (oral) will be measured, and a trained member of the site study staff will dispense the tablet(s) constituting the assigned dose to the subject.
- The site staff must observe the subjects for at least 30 minutes after study drug administration for any acute reactions. Any acute reactions are to be recorded in the subject's source documents, on the AE page of the eCRF, as applicable.
- Subjects will be asked to record symptoms of reactogenicity daily for 1 week after study drug administration on Day 1, using the Solicited Symptom Diary; the Solicited Symptom Diary will be collected from the subject on Day 8 and reviewed.
- Subjects will be queried for unsolicited AEs for 28 days following the study drug administration and for SAEs, AESIs and NOCIs for 1 year following the study drug administration.
- Subjects will return to the site on Day 8 and Day 29:
 1. Blood, nasal, and saliva samples will be collected for immunogenicity assessment on Day 8 and Day 29 as specified in the SoA ([Table 1](#)).
 2. Ascertain if the subject is still breastfeeding. Ensure the subject has also collected breastmilk sample and infant stool sample during the timepoints specified in the SoA ([Table 1](#)), if not then remind the subject. Review with the subject how the collection was done and if the samples were properly stored.
 3. Verify understanding of and compliance with protocol requirements for contraception (see [Appendix 4](#)).
- The subject will be asked to contact the site staff or Investigator if an AE (e.g., doctor's visit, emergency room visit) or hospitalization occurs.

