
Section 7.1.1. Procedure to be followed on Screening Period (Day -45 to Day -1)
	
Current Text
 
The subject can use a manual breast pump if she does not wish to manually express her breastmilk.
 
Timepoints for breastmilk and infant stool sample collection must be thoroughly discussed with the subject. The subject must collect breastmilk sample and infant stool sample at baseline prior to the first dose (Day -2 to Day 1).
 
Updated Text:
 
The subject can use a manual or electric breast pump if she does not wish to manually express her breastmilk.
 
Timepoints for breastmilk and infant stool sample collection must be thoroughly discussed with the subject. The subject must collect breastmilk sample and infant stool sample (15ml) at baseline prior to the first dose (Day -2 to Day 1).
 
Removed text:
 
Teach the subject how to properly freeze her milk after expression each time until all samples are collected and shipped.
	
Allow more flexibility for methods subject can use to provide breastmilk samples
 
Breastmilk will be collected on site instead of home due to difficulty collecting and storing breastmilk properly and difficulty with transport of home collection to site in the required timeframe
 
Provided volume of stool sample required.

7.1.2 Procedure to be followed during Active Study Period (Day 1 to Day 29)	
Current Text:
 
...breastmilk sample (5ml-10ml)
 
...and to remind the subjects to collect and store breastmilk samples
 
Updated Text:
 
Ensure the subject collected baseline breastmilk sample (10ml) and infant stool sample between D-2 to D1.
 
Removed Text:
 
deleted "5ml"
 
deleted "and to remind the subjects to collect and store breastmilk samples."
	Subjects not required to collect breastmilk samples at home due to logistics as mentioned previously

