**Figure 1: Study Design**

After vaccination on Day 1, the study will include an Active Study Period that runs through 4 weeks after administration (Day 29), and a Follow-up Period of one-year post-dose for safety and duration of immune response. Study assessments will be conducted as shown in the SoA (Table 1). In addition, subjects will be contacted by phone between site visits to monitor for safety as specified in the SoA (Table 1).

A subject is considered to have completed the study if she completes the study active period at Day 29 (End of Study Active Period). Following completion of the Day 29 visit by all subjects the database will be cleaned and locked and the study unblinded, except the medical monitoring and pharmacovigilance team including anyone at the Sponsor, CRO and sites(s). The Topline Clinical Study Report (CSR) will be written based on the Day 29 clean datasets.

A subject is considered to have completed the Follow-up Period if she remains in the study through Day 365 (Month 12). Following completion of the Day 365 tele-health appointment for all subjects, the safety database will be cleaned and locked, and data collected during the Follow-up Period will be included in a CSR addendum.

All subjects will be monitored for Solicited Symptoms of Reactogenicity (GI and systemic) for 1 week following the study drug dose (until Day 8 (+2 days) scheduled site visit) and unsolicited AEs for 28 days post study drug dose (until Day 29 scheduled site visit) during the active period. Subjects will then enter the Follow-up period after Day 29 and will be monitored for specified unsolicited adverse events (SAEs, AESIs, and NOCIs) through Day 365 (Month 12) for safety and durability of immune response. Subjects will provide samples (nasal, saliva, serum, breast milk, and infant stool for evaluation of immunogenicity as specified in the Schedule of Activities (SoA) (Table 1).

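### Protocol v2.0 is only half amended on where breast milk is collected, so the baseline and post-dose milk behind the primary fold rise could be handled differently

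*Protocol*

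**What the plan says.** The operative sections of protocol v2.0 describe self-collection throughout.

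- Section 4.1: women "will also self-collect samples (breastmilk and infant stool) at home for evaluation of immunogenicity".
- Section 7.1.1: the site is to "Provide kits with instructions for breastmilk sample collection, storage, and return", and "The subject must collect breastmilk sample and infant stool sample (15ml) at baseline prior to the first dose", within a window of Day -2 to Day 1.
- Section 7.1.2, before dosing: "Ensure the subject collected baseline breastmilk sample (10ml) and infant stool sample between D-2 to D1". The site then reviews how the sample was taken and stored. "If this was not done, the subject will need to reschedule the dosing visit ASAP and be reminded to collect baseline samples".
- Section 7.1.2, Days 8 and 29: "Ensure the subject has also collected breastmilk sample and infant stool sample during the timepoints specified in the SoA", again with a review of storage. Section 7.1.3 repeats this for Days 60 and 180 in women still breastfeeding.

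Appendix 6 gives the sponsor's reason for the v2.0 text of 7.1.1: "Breastmilk will be collected on site instead of home due to difficulty collecting and storing breastmilk properly". It adds that transport from home in the required time was difficult. For 7.1.2 and 7.1.3 it likewise says milk is no longer to be collected at home. The instruction to teach women to freeze their milk is listed as removed, and it is absent from the v2.0 body. The milk samples on Days 15 and 120, both telephone contacts, were dropped from Table 1.

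The SAP (section 2.1) does not say where milk is collected: "Subjects will provide samples (nasal, saliva, serum, breast milk, and infant stool for evaluation of immunogenicity". Under SAP section 3.2, baseline is the last valid value before vaccination. SAP section 14 divides each post-dose concentration by that value.

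**The concern.** The body and the stated intent of the same protocol version point to different places of collection. One reading uses milk expressed and stored at home, which the sponsor itself found hard to do properly. The other uses milk expressed at the clinic. A site could also combine them: a home baseline on Day -2 or Day -1, when no visit is scheduled, followed by milk expressed at the Day 8 and Day 29 visits.

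Milk GMFR and fold-rise counts are primary endpoints, and the primary immunogenicity objective singles out the milk response as the most critical part. Each woman's fold rise has her baseline sample as its denominator. If the two samples differ in handling, any difference in recovered signal goes straight into the fold rise and looks like a vaccine effect, or hides one. The SAP has no flag, listing or sensitivity analysis by place of collection. Its section 3.1 also applies no windows to exclude assessments.

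**Working it through.** **1. Is the conflict in current text?** An entry in a change log that differs from the text is not an error by itself, so the operative text and schedule have to carry the point.

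| Item in v2.0 | Fits home | Fits on site |
|---|---|---|
| 4.1, self-collection at home | yes | no |
| 7.1.1, milk kits for storage and return; Day -2 to Day 1 baseline | yes | no |
| 7.1.2 and 7.1.3, check that milk was already collected and stored | yes | no |
| Freezing instruction absent from 7.1.1 | no | yes |
| Table 1, milk on Days 1, 8, 29, 60 and 180 only | either | yes |
| Appendix 6, reasons given for the v2.0 text | no | yes |

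Table 1 shows telephone contacts on Days 15, 120, 240, 300 and 365. None is now a milk day, so all five milk days are site visits. Part of the move on site has been carried into the operative text and part has not.

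**2. Could a home baseline enter the analysis?** Yes. The Day -2 to Day 1 window permits it, and the SAP baseline rule accepts any last valid pre-dose value.

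**3. What would a mismatch do?** The documents give no recovery figure and no SD for the fold rise, so there is no plan figure to reproduce. What follows is illustration under stated assumptions.

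Observed fold rise = true fold rise × (post-dose recovery / baseline recovery).

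Milk results are expressed per µg of total IgA (SAP section 18). Recovery here therefore means recovery of VP1-specific signal relative to total IgA; equal loss of both cancels.

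Assume no true rise and the same mismatch in every woman in an arm:

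- baseline at 80% of post-dose recovery: GMFR × 1/0.80 = 1.25;
- post-dose at 80% of baseline recovery: GMFR × 0.80.

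If only half the women are mismatched, the factors shrink to √1.25 = 1.12 and √0.80 = 0.89.

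For the responder count at one visit, with b the GMFR factor and SD the assumed SD of the log10 fold rise:

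P(fold ≥ 2) = 1 − Φ[(log10 2 − log10 b)/SD].

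Example: b = 1.25 and SD = 0.2 give (0.301 − 0.097)/0.2 = 1.02, so P = 15.4%.

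| Assumed SD | Same handling (b = 1) | Baseline worse (b = 1.25) | Post-dose worse (b = 0.80) |
|---|---|---|---|
| 0.2 | 6.6% | 15.4% | 2.3% |
| 0.3 | 15.8% | 24.8% | 9.2% |
| 0.4 | 22.6% | 30.5% | 16.0% |

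In an arm of 30 at SD 0.2, that is about 2.0, 4.6 and 0.7 women (30 × 0.066, 30 × 0.154, 30 × 0.023). The first column is noise alone; handling moves the count either way from there.

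**The case against.** The best defence is that 4.1 and 7.1.1 to 7.1.3 agree with one another. Read literally, they treat baseline and post-dose milk alike: the woman collects, and the site reviews collection and storage. On-site collection is stated only in the change table. That stands in part. No passage instructs a mix, and a mismatch is a possibility, not a described procedure. It does not clear the plan, because following the body means using handling that the sponsor called difficult, while the schedule has already been cut to site visits.

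Four stronger readings are tempting, and the documents do not support them.

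- *Home milk is left without storage instructions.* Only the freezing sentence in the body is gone. The kits carry storage instructions, and sections 7.2.1 and 8.2.3 defer further detail to laboratory manuals that are not supplied.
- *The fold rise will be inflated.* That holds only if the baseline is the worse-handled sample. The reverse lowers it.
- *One arm will be favoured.* Collection rules are common to all arms, and women and investigators are blinded. Placebo is tabulated too, so a shared artefact should appear there. The limits are that placebo has 16 women, no formal comparison is planned (SAP section 3.3), and the SAP text describes the antibody charts for the two active arms.
- *Sites are currently working to contradictory orders.* The SAP cites a clarification memorandum of January 2024 that is not supplied and may cover this.

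**Conclusion.** The point holds as an incomplete amendment that leaves the denominator of a primary endpoint exposed. Protocol v2.0 lets sites follow home collection, on-site collection or a mixture, and neither document secures the same handling within a woman's baseline and post-dose pair. The results at risk are the within-arm milk GMFR and fold-rise counts.

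The size is unknown. The factors of 1.25 and 0.80 rest on an assumed 20% recovery difference affecting every woman in the arm, and the responder rates also rest on assumed SDs of 0.2 to 0.4. Normalising to total IgA may offset part of any loss, but the documents do not show that specific and total IgA are lost equally. The change is worth making because it is cheap and the milk response is central. The documents do not show that bias has occurred.

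**What to change.** **Protocol.** Make 4.1 and 7.1.1 to 7.1.3 agree with the stated on-site intent: milk expressed at the Day 1 visit before dosing, and at the Day 8, 29, 60 and 180 visits. Take milk out of the home-collection sentence, and keep the home kit and the Day -2 to Day 1 window for infant stool only. If the January 2024 memorandum already settles this, carry its wording into the protocol and SAP.

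**eCRF.** Record place, date and time of expression for each milk sample.

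**SAP section 14.** Flag home-collected milk. If there is any, repeat the primary milk GMFR and responder tables in baseline/post-dose pairs with the same handling, for placebo as well as the active arms. Samples already taken can be flagged where source records show where they were expressed.

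**Cost.** No visit is added. Visits become slightly longer, the baseline sample loses some flexibility (a woman who cannot express milk on Day 1 would face a rescheduled dosing visit), the place, date and time entry is added to the eCRF, and there is one extra set of tables.

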3.2.2. Secondary End Points

- **Safety**

- Frequency, duration, and severity of all SAEs, AESIs, and NOCIs through 12 months after last study drug dose

- **Immunogenicity**

- Serum VP1 specific (GI.1 and GII.4) IgA through 6 months after study drug dose measured by Meso Scale Discovery (MSD) assay by dose level
 - Geometric mean concentration (GMC) at Day 180
 - Geometric mean fold rise (GMFR) from Day 1 to Day 180
- Breastmilk VP1 specific (GI.1 and GII.4) IgA through 6 months after study drug dose measured by Meso Scale Discovery (MSD) by dose level
 - Geometric mean concentration (GMC) at Day 60 and Day 180
 - Geometric mean fold rise (GMFR) from Day 1 to Day 60 and from Day 1 to Day 180
- Serum VP1 specific (GI.1 and GII.4) IgG through 6 months after study drug dose measured by Meso Scale Discovery (MSD) assay by dose level
 - Geometric mean concentration (GMC) at Day 1, Day 8, Day 29, and Day 180
 - Geometric mean fold rise (GMFR) from Day 1 to Day 8, from Day 1 to Day 29, and from Day 1 to Day 180
- Serum Blocking titers 50 (BT50) (GI.1 and GII.4) through 6 months after study drug dose measured by Histo-blood group antigen (HBGA) assay by dose level
 - Geometric mean titer (GMT) at Day 1, Day 8, Day 29, and Day 180
 - Geometric mean fold rise (GMFR) from Day 1 to Day 8, from Day 1 to Day 29, and from Day 1 to Day 180

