4.4 End of the Study Definition

A subject is considered to have completed the study if he/she completes the study active period at Day 29 (End of Study Active Period). Following completion of the Day 29 visit by all subjects the database will be cleaned and locked, and the study unblinded. The CSR will be written based on the Day 29 dataset.

A subject is considered to have completed the Safety Follow-up Period if he/she remains in the study Day 365 (Month 12). Following completion of the Day 365 tele-health appointment of all subjects, the safety database will be cleaned and locked, and data collected during the Follow-Up Period will be used to generate a CSR addendum.

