8.1 Safety Assessment

The safety of the bivalent GI.1 and GII.4 vaccines will be evaluated through the reporting of Solicited Symptoms of Reactogenicity (GI and systemic) for 1 week following the study drug dose and through reporting of frequency, duration, and severity of unsolicited AEs for the next 28 days following the study drug dose. The subjects will then enter the Follow-Up Period after Day 29 and will be monitored for SAEs, AESIs, and NOCIs through Day 365 (Month 12) for safety and duration of immune response. Each SAE, AESI, and NOCI occurrence must be assessed for causality.

AESIs are listed in [Appendix 5](#), the occurrence of these events should be reported to the Sponsor in an expedited manner, similar to SAEs as described in [Section 9](#).

Planned time points for all safety assessments are provided in the SoA ([Table 1](#))

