#### 3.1 General Considerations

All data collected on the electronic case report form (eCRF) will be presented in the data listings and will be sorted by treatment arm, subject number and visit, where applicable. All descriptive summaries will be presented by treatment arm and nominal visit.

All safety and immunogenicity descriptive summaries will be presented by treatment arm and nominal visit.

Unless otherwise stated, the following methods will be applied:

- Continuous variables: Descriptive statistics will include the number of non-missing values (n), arithmetic mean, standard deviation (SD), median, minimum and maximum values.

The minimum and maximum values will be displayed to the same decimal precision as the source data, the arithmetic mean, SD and median values will be displayed to one more decimal than the source data for the specific variable.

95% Confidence Intervals (CIs), mean differences (among treatments and from baseline) and least-square (LS-Means) values will be displayed to one more decimal than the source data for a specific variable. P-values will be displayed to 3 decimal places.

The appropriate precision for derived variables will be determined based on the precision of the data on which the derivations are based, and statistics will be presented in accordance with the above-mentioned rules.

- Categorical variables: Descriptive statistics will include counts and percentages per category. The denominator in all percentage calculations will be the number of subjects in the relevant analysis population with non-missing data, unless specifically stated otherwise. Percentages will be displayed to one decimal place. Proportions will be displayed to 3 decimal places.

95% Confidence Intervals (CIs), difference in proportions and other categorical parameters will be displayed to one decimal place for percentages. Proportions will be displayed to 3 decimal places. p-values will be displayed to 3 decimal places.

- Repeat/unscheduled assessments: Only values collected at scheduled study days/time points will be presented in summary tables. If a repeat assessment was performed, the result from the original assessment will be presented as the result at the specific visit/time point. All collected data will be included in the data listings.

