**16. INTERIM AND FINAL ANALYSIS**

A principal statistical analysis will be performed after all subjects have completed the active period of the study up to Day 29 post-vaccination, the subject database has been locked, the analysis set of populations will be approved, and the study will be unblinded except the medical monitoring and pharmacovigilance team including anyone at the Sponsor, CRO and sites(s). The principal Clinical Study Report (CSR) will be written after this analysis. If any exploratory parameters are available, Vaxart will keep them for possible future analysis. A final statistical analysis will be performed after all subjects have completed the long-term follow-up phase of the study up to Day 365 post-vaccination and safety dataset has been locked. An addendum to the principal CSR will be written after this analysis.

The final analysis will be based on the final version of SAP.

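### The protocol and SAP disagree on who stays blind after the Day 29 lock, so a substantial part of the 12-month safety follow-up may be collected open-label

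*Protocol*

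**What the plan says.** Protocol 4.1: "Following completion of the Day 29 visit by all subjects the database will be cleaned and locked and the study unblinded". Protocol 4.4 gives the same trigger: "Following completion of the Day 29 visit by all subjects the database will be cleaned and locked, and the study unblinded". Neither names anyone who stays blind. The clinical study report is then written on Day 29 data, and follow-up to Day 365 goes into an addendum after a second lock.

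SAP 2.1 departs from this: "the study unblinded, except the medical monitoring and pharmacovigilance team including anyone at the Sponsor, CRO and sites(s". SAP 16 repeats it: "the study will be unblinded except the medical monitoring and pharmacovigilance team including anyone at the Sponsor, CRO and sites(s". SAP 15, which lists changes to the planned analysis, does not mention the exception.

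Protocol 6.7.2 blinds subjects, investigators, site personnel and the Sponsor to individual assignment. It exempts the pharmacist preparing doses and designated Sponsor staff, including those doing bioanalysis. It sets no date on which blinding ends.

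After Day 29 the trial still collects a secondary safety endpoint, "Frequency, duration, and severity of all SAEs, AESIs, and NOCIs through 12 months after last study drug dose", and Protocol 8.1 adds: "Each SAE, AESI, and NOCI occurrence must be assessed for causality". Serum and breastmilk are sampled at Day 180, and breastmilk also at Day 60.

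**The concern.** A site reading these documents cannot tell whether it, or the woman it is following, should still be blind between the Day 29 lock and Day 365.

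This matters most for safety. Protocol 11.1 gives safety comparison as the reason for the placebo arm. The long-term endpoint involves judgement: whether a complaint is reported and pursued to a diagnosis, and whether the investigator calls it related. SAP 18 plans Day 30 to 365 tables of SAEs, NOCIs and AESIs by relationship and arm. Four of the six follow-up contacts (Days 120, 240, 300 and 365) are telephone calls, so they rely on what the woman says. If she or the investigator knows she had placebo, reporting and attribution could differ between arms.

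Day 180 milk raises a second, smaller issue. Eligibility asks for planned breastfeeding of only one month, and later milk depends on the woman still breastfeeding. Knowing her assignment could affect whether she continues to supply samples.

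**Working it through.** **Step 1. Compare the texts on who is blind after the Day 29 lock.**

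| Text | Participants | Investigators and site staff | Medical monitoring and pharmacovigilance |
|---|---|---|---|
| Protocol 4.1, 4.4 | unblinded (no exception) | unblinded (no exception) | unblinded (no exception) |
| SAP 2.1, 16, narrow reading | not mentioned | unblinded unless on the exempt team | blind |
| SAP 2.1, 16, broad reading | not mentioned | blind | blind |
| Protocol 6.7.2 | blind, no end date | blind, no end date | Sponsor blind, no end date |

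The rows conflict. The broad reading also leaves open who at the Sponsor or CRO would hold the codes needed to produce Day 29 tables by arm.

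**Step 2. How much follow-up lies after unblinding.** The documents state no such share, so there is no figure to reproduce. They fix the trigger (last woman's Day 29, plus cleaning and lock) and the end (Day 365). The accrual period E and lock lag L are my assumptions: E = 3 to 6 months, L = 1 to 3 months, uniform entry, full retention.

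Unblinding falls at calendar month E + 1 + L. A woman entering at month t then has t + 12 − (E + 1 + L) months left.

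- Last woman (t = E): 11 − L, which is 10 months at L = 1 and 8 at L = 3.
- First woman (t = 0): 11 − E − L, which is 7 months at E = 3, L = 1 and 2 at E = 6, L = 3.
- Average: 11 − E/2 − L. At E = 3, L = 1 this is 8.5 of 12 months (71%). At E = 6, L = 3 it is 5 of 12 (42%).

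**Step 3. Day 180 visits.** A month-6 visit falls after unblinding if t + 6 > E + 1 + L, that is t > E + L − 5.

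| E | L | Condition | Share after unblinding |
|---|---|---|---|
| 3 | 1 or 2 | every t | 100% |
| 3 | 3 | t > 1 | 2/3 = 67% |
| 6 | 2 | t > 3 | 3/6 = 50% |
| 6 | 3 | t > 4 | 2/6 = 33% |

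**Step 4. Day 60 visits.** The condition is t + 2 > E + 1 + L, that is t > E + L − 1. For L of one month or more, no nominal Day 60 visit meets it. In days, a lag of 30 puts the last woman at 29 + 30 = Day 59 when the blind is broken, so only the last few enrolled could be affected within the ±7-day window.

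**Step 5. Wider range.** Let accrual A run from 0 to 365 days and lag L from 0 to 120 days. A woman enrolled u days before the last one has max(0, 365 − (29 + u + L)) days after unblinding.

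| A (days) | L (days) | Share of 365 days | Share of Day 180 visits |
|---|---|---|---|
| 0 | 0 | 92.1% | 100% |
| 90 | 30 | 71.5% | 100% |
| 120 | 60 | 59.2% | 75.8% |
| 180 | 60 | 51.0% | 50.6% |
| 180 | 90 | 42.7% | 33.9% |
| 365 | 120 | 17.5% | 8.5% (about 6 of 76) |

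The top row is the ceiling: 365 − 29 = 336, and 336/365 = 92.1%. It needs every woman to be unblinded at her own Day 29. The safety share reaches 50% when 336 − A/2 − L = 182.5, that is A + 2L = 307 days. Some safety time and some Day 180 visits fall after unblinding in every case tested.

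**The case against.** A reader might infer that most of the 12-month endpoint, even 92% of it, is open-label. The documents do not support that. Unblinding waits for the last woman's Day 29 and then for lock. With six months of accrual and three to lock, less than half of follow-up lies beyond it.

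A reader might also take open-label collection as settled. It follows from Protocol 4.1 and 4.4 or from the narrow SAP reading. Under the broad reading sites stay blind, Protocol 6.7.2 still lists subjects as blinded, and no text describes telling participants their arm. Nor will the Day 29 report necessarily unblind sites. SAP 3.1 says "All data collected on the electronic case report form (eCRF) will be presented in the data listings and will be sorted by treatment arm", but nothing sends those listings to sites; equally, nothing restricts them.

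Other limits are fair:

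- Primary safety data and the Day 1 to Day 29 primary samples are collected before unblinding.
- The analysis is descriptive, with no hypothesis testing (SAP 3.3).
- NOCIs are defined as diagnoses and AESIs are largely listed conditions, so they are less open to suggestion than plain symptoms. Two follow-up contacts are site visits.
- Day 180 IgA and IgG are laboratory assays, and designated staff already hold codes for bioanalysis, so Day 29 unblinding adds little measurement bias.
- An effect of assignment on breastfeeding is plausible, but the documents do not evidence it.
- SAP 21 cites a protocol clarification memorandum that is not available here. Whether it addresses blinding cannot be checked.

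These points reduce the size and certainty of the concern. They do not remove the conflict between the texts, or the silence in the SAP exception about participants.

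**Conclusion.** The concern holds as a conflict about blinding after the Day 29 lock, with a conditional consequence. If the protocol text or the narrow SAP reading governs, a substantial part of the placebo-controlled SAE, AESI and NOCI follow-up, including causality opinions, is open-label. The size is about 42 to 71% of the 12 months under 3 to 6 months of accrual and 1 to 3 months to lock, and 17.5 to 92.1% over the wider range. The corresponding shares of Day 180 visits are 33 to 100% and 8.5 to 100%. All of these figures assume uniform accrual, full retention, and that sites and participants are in fact told. Day 60 sampling is almost unaffected once the lock lag reaches a month. At Day 180 the issue is mainly who keeps supplying samples. If the broad SAP reading governs, site assessment stays blind, and what remains is the unstated position of participants and of by-subject listings.

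**What to change.** Reconcile Protocol 4.1, 4.4 and 6.7.2 and SAP 2.1 and 16 to one rule stated by role:

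- At the Day 29 lock, individual treatment codes go only to a named analysis group with no site contact.
- Participants, investigators, site staff other than the unblinded pharmacist, and the medical monitoring and pharmacovigilance team stay blind to individual assignment until the Day 365 lock.
- The existing provisions for emergency unblinding, SUSAR unblinding, SMC review of unblinded data and designated bioanalysis staff stay in place. The text should say how the Medical Monitor's seat on the SMC (Protocol 10.2) fits the rule.
- By-subject listings that show the arm are withheld from blinded roles until the Day 365 lock. The Day 29 report can go to them with group-level tables.
- The addendum reports how much follow-up, and how many Day 180 visits, came after the Day 29 unblinding.
- SAP 15 records the departure from the protocol if the protocol is not amended.

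The cost is wording in five sections, a line on the SMC and an access list. The Day 29 analysis keeps its timing. The downside is that sites and participants learn assignments later, and some readers wait for the listings.
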